# 5 STUDY OBJECTIVES

#### 5.1 PRIMARY OBJECTIVES:

#### **Dose Escalation Part**

• To determine the maximum tolerated dose (MTD)/maximum administered dose (MAD) of SAR440234 administered as a single agent in patients with R/R AML, HR-MDS, or B-ALL and determine the recommended Phase 2 dose (RP2D) for the subsequent Expansion Part.

# **Expansion Part**

• To assess the activity of single agent SAR440234 at the RP2D in patients with R/R AML or HR-MDS.

#### 5.2 SECONDARY OBJECTIVES:

- To characterize the safety profile of SAR440234 including cumulative adverse drug reactions.
- To characterize the pharmacokinetic profile of SAR440234 when administered as a single agent.
- To evaluate the potential immunogenicity of SAR440234.
- To assess any preliminary evidence of hematologic response in the Dose Escalation Part.

# 5.3 EXPLORATORY OBJECTIVES:

To perform pharmacodynamic assessments on blood and bone marrow including:

- To measure CD123 expression in malignant cells and kinetics of this expression under treatment.
- To monitor CD123 expression on normal cells.
- To assess minimal residual disease (MRD) in patients achieving a complete response (CR) or complete response with incomplete hematological recovery (CRi), and correlate MRD with clinical outcome.
- To assess T-cell subpopulations (eg, CD4, CD8) and activation status.
- To investigate the relationship between CD123 expression, disease molecular subtype (as defined by marker expression, cytogenetics, and/or genomics) and parameters of clinical response.

To assess levels of cytokines following treatment administration, and their relationship with safety profile and clinical outcome.

# 6 STUDY DESIGN

#### 6.1 DESCRIPTION OF THE STUDY

# **Sequential cohort(s):**

This Phase 1/2A Study is an open-label, nonrandomized, dose escalation and dose expansion, safety, efficacy, pharmacokinetic, and pharmacodynamic evaluation study of SAR440234 administered as a single agent IV infusion every week to patients ≥16 years of age with R/R AML, HR-MDS, or B-ALL.

The study will be performed in 2 parts: a Dose Escalation Part and an Expansion Part both with SAR440234 used as monotherapy. Enrollment of patients in the Expansion Part will start after completion of the Dose Escalation Part and identification of the MTD/RP2D.

#### 6.2 STARTING DOSE AND DOSE ESCALATION PART

The rationale for selecting the starting dose and the dose escalation design are described in Section 4.5.1 and in Section 1.1, respectively.

# 6.2.1 Starting dose and dose levels

SAR440234 will be administered IV on Day 1, Day 4 (DL≥3), Day 8, and weekly thereafter in Cycle 1 for a 42-day cycle. The dosing regimen will be weight-based; however, if a patient weighs >140 kg, the patient's weight will be capped at 140 kg for dose calculations. The administration of the investigational medicinal product (IMP) will begin at the selected safe starting dose for an FIH trial, based on the MABEL, and by integration of all available in vivo and in vitro data at the start of the study.

A 3+3 dose escalation scheme will be used, based on DLTs observed during the first 42 days following the first administration of IMP in the first cycle (the DLT observation period). The goal is to treat 3patients per dose level in order to follow a 3+3 design. In this FIH study, potential DLTs are defined as the following:

• Any Grade ≥3 nonhematological AE, unless either caused by disease progression or an obviously unrelated cause or caused by a laboratory abnormality without associated clinical consequences that resolves within 5 days (AE's related to cytopenias that were present prior to starting SAR440234 or to underlying leukemia will not be considered DLT's).

- Grade 4 hematological toxicities as defined in NCI-CTCAE v4.03, ie, new onset or
  worsening of life-threatening hematological abnormalities after administration of
  SAR440234 (AE's related to cytopenias that were present prior to starting SAR440234 or
  to underlying leukemia will not be considered DLT's).
  - Grade 4 bone marrow hypocellularity, if not caused by disease progression and not improved to baseline value or Grade ≤1 within 14 days,
  - Grade 4 decreased neutrophils, if not present at baseline and not resolved to baseline value or Grade ≤1 within 14 days,
  - Grade 4 febrile neutropenia not resolved within 7 days,
  - Grade 4 decreased platelet count, if not present at baseline and not improved to baseline value or Grade ≤1 within 14 days,
  - Grade 4 anemia, if not improved to baseline value or Grade ≤1 within 14 days.
- Grade 3 or Grade 4 CRS.
- Grade 2 CRS if it persists for >48 hours or is present <48 hours before the time when the next planned dose of SAR440234 is due.
- Any treatment-emergent adverse event (TEAE) that, in the opinion of the Principal Investigator and Sponsor, is of potential clinical significance such that further dose escalation would expose patients to unacceptable risk.
- IMP-related adverse reaction (unless caused by disease progression or an obviously unrelated cause) lasting more than 2 weeks with failure to recover to baseline or improve to Grade <1.

During the Dose Escalation Part, escalation to the next dose level cohort will occur after the last patient has completed the DLT observation period for the previous dose level. Within a dose level, subsequent patients will initiate treatment at least 1 week after the first patient in that dose level started treatment with SAR440234.

The occurrence of DLTs will inform the dose recommendation that will be used during the Expansion Part.

Response will be evaluated by a bone marrow aspirate at the end of Cycle 1 (Day 42 ±2 days). Patients may continue treatment with the IMP as long as clinical benefit is possible, or until disease progression, unacceptable adverse reaction, patient's decision to stop the treatment, or other reason for discontinuation (Section 6.5). Bone marrow aspirate will be performed on Day 42 (±2 days) of Cycle 2. Additional bone marrow aspirate is required if onset of cytopenia >14 days before or after Day 42. Subsequent bone marrow aspirates will be performed when clinically indicated, as determined by the treating physician. Additional bone marrow aspirate shall be performed as clinically indicated or if any of the following occurs: if decreased neutrophil count Grade 4, decreased platelet count Grade 4, febrile neutropenia Grade 3 and Grade 4, or anemia Grade 4 occurs with onset in >14 days before or after Day 42.

Response assessment will be performed according to the International Working Group (IWG) 2003 recommendations for AML (19) and the revised 2000 criteria for HR-MDS (34), and the 2016 National Comprehensive Cancer Network (NCCN) Guidelines for ALL (Appendix D, Appendix F, and Appendix H).

If at the end of a cycle the patient exhibits clinical benefit by symptoms or response criteria and does not meet study treatment discontinuation criteria, the patient may continue therapy until an unacceptable AE, disease progression, patient's decision to stop the treatment, or any other reason.

To minimize the risk of severe CRS, an intra-patient dose escalation in Cycle 1 is proposed, as shown in Table 1. Lead-in doses include the first 2 doses in DL1 and DL2 (ie, Week 1 and Week 2 administered doses), the first 3 doses in DL3 to DL5, and the first 4 doses in DL6 to DL8. After the lead-in doses, each patient will receive a fixed dose until the end of treatment, unless the dose needs to be decreased for safety reasons. DL1 to DL8 will achieve a range of lead-in doses from and a range of final doses from During each cycle, pharmacokinetic and pharmacodynamic data will be collected that will be used, together with acute safety monitoring, in both the Dose Escalation and Expansion Parts.

Cycle 1 (doses in ng/kg) **Dose Level** Week 1 Week 2 Week 3 Week 4 Week 5 Week 6 Day 15 Day 29 Day 36 Day 1 Day 4 Day 8 Day 22 DL1 DL2 DL3 DL4 DL5 DL6 DL7

Table 1 - Intra-patient dose escalation: Cycle 1

DL=dose level

DL8

For subsequent cycles, patients will maintain the maximum weekly dose that they achieved in Cycle 1, as shown in Table 2.

Table 2 - Patient dosing after Cycle 1

			Cycle ≥2 (do	ses in ng/kg)		
Dose Level	Week 1	Week 2	Week 3	Week 4	Week 5	Week 6
DL1						
DL2						
DL3						
DL4						
DL5						
DL6						
DL7						
DL8						

DL=dose level

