#### Study continuation

The duration of each cycle of treatment is 42 days, with weekly administration of IMP (except for Cycle 1 Week 1 in DL ≥3 when 2 administrations will be given).

In the Dose Escalation Part, at the end of Cycle 1, 43 days after the first SAR440234 infusion, a patient may begin Cycle 2 provided he or she did not experience a DLT. The dose given in the second or subsequent cycles will be the last dose given in the previous cycle.

If severe toxicity occurs, dose reduction, omission, treatment delay, and/or treatment discontinuation are planned (details are provided in Section 6.5).

A Study Committee, including the main Investigators, Sponsor clinical team, and ad hoc experts, when appropriate, will regularly review the safety data, and will make recommendations as appropriate.

Additional (optional) cohort(s) beyond DL8, or intermediate dose levels, may be evaluated; the decision to proceed with these optional cohort(s), however, will be discussed with the Study Committee and based on the available safety, exploratory, and pharmacokinetic data.

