# **Study continuation**

The duration of each cycle of treatment is 42 days, with weekly administration of IMP (except for Cycle 1 Week 1 in DL  $\geq$ 3 when 2 administrations will be given).

The criteria for retreatment of patients are described in Section 6.5.

The dose given in the second or subsequent cycles will be the last dose given in the previous cycle. If there is a  $\geq$ 10-day interval between administrations of SAR440234, the next infusion must start with the lead-in doses appropriate for the selected dose level.

Additional pharmacokinetic data, safety and disease response will be assessed as indicated in the flow charts (Section 1.2) and when clinically indicated.

A Study Committee including the main Investigators, Sponsor's clinical team, and ad hoc experts, when appropriate, will regularly review the safety data, and will make recommendations as appropriate. The Study Committee will also decide the RP2D, including the recommended lead-in dose and schedule, for the Expansion Part in R/R AML and HR-MDS patients.

Additional (optional) cohort(s) beyond DL8, or intermediate dose levels, may be evaluated; the decision to proceed with these optional cohort(s), however, will be discussed with the Study Committee and will be based on the available safety, exploratory, and pharmacokinetic data.

It is anticipated that the number of patients enrolled in the Dose Escalation Part will be 30 to 40.

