#### 6.5.2 Dose modifications

When more than 1 AE is present, treatment modifications will be in accordance with the guidelines for the most severe AE.

Dose modifications, if required, will be a reduction of 1 step (Table 4) from the last administered dose. For example, if the last administered dose was (Step 5), a 1 step dose reduction would be to (Step 4). Otherwise, the lead-in dose will be based on the last administered dose.

Step Target Dose (ng/kg)

Lead-in Dosing When Restarting Treatment (if Applicable)

[figure not shown]
1
2
3
4
5
6
7
8
9
10

Table 4 - Definition of dose steps

IV=intravenous

11

The target dose is the dose that will be given every 7 days after lead-in dosing. When there is a dose delay of 2 days (ie, <10 days from the last infusion), the dose may be given without the lead-in dose.

If an AE requiring dose reduction and lead-in dosing occurs following the dose, the 1 ng/kg weekly dose will be administered.

If an AE requiring dose reduction occurs following the dose, the IMP will be discontinued.

After a safe and effective dose has been defined, individual patients who are still on study treatment at a different dose may be considered for treatment at another dose or schedule from which they were originally assigned, if this dose and schedule is thought to be safer and/or more effective, and the Sponsor and Investigator agree that it would be beneficial for the patient. If the dose exceeds the originally assigned dose, lead-in dosing will be administered.

Property of the Sanofi Group - strictly confidential

Page 59

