Grade a	After SAR440234	Infusion completed			
	Duration of event <48 hours and event resolved >48 hours before next dose is due	Duration of event >48 hours and/or persistent <48 hours before next dose is due			
1	Administer the next dose when planned and escalate the dose (if planned).				
2	Administer the next dose when planned, but do	Omit next dose.			
	not escalate next dose. If tolerated well, dose escalation may resume subsequently.	After AE resolved, restart treatment. Dose reduction by 1 step must be applied (Table 4). Treatment will restart with the lead-in dose.			
		The reaction is a DLT if CRS occurs during Cycle 1.			
		If CRS Grade >2 persists for >14 days after the last infusion, SAR440234 will be permanently discontinued.			
3	Omit ne	ext dose.			
	After AE resolved, restart treatment. Dose reduction by 1 step must be applied (Table 4). Treatment w restart with the lead-in dose. Do not escalate past the target dose.				
	The reaction is a DLT if CRS occurs during Cycle 1				
		or if it recurs again, treatment will be permanently ntinued			
4	Permanent d	iscontinuation.			

a Grade of CRS according to the 2014 National Cancer Institute Consensus Guidelines (Appendix H) AE=adverse event, CRS=cytokine release syndrome, DLT=dose-limiting toxicity

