### Grade 3:

- If the AE is resolved before the time of the next scheduled infusion, or within ≤10 days after the last infusion, treatment will be continued with a dose reduction of 1 step (Section 6.5.2) after recovery.
- If the AE is resolved in 10 to 14 days after the last infusion, omit 1 dose. After recovery, treatment will resume with dose reduction by 1 step. Treatment will restart with the lead-in dose
- If the AE is not resolved in ≤14 days after the last infusion, treatment will be permanently discontinued.
- If the patient experiences a second episode of the same AE, the study treatment will be permanently discontinued.

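### The protocol gives two rules for the dose from Cycle 2 on, and they differ for any patient whose last dose was not the Cycle 1 maximum

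*Protocol*

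**What the plan says.** Two sentences govern the dose after Cycle 1, and each stands in both the synopsis and the body of the current protocol.

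- **Rule A** (Section 6.2.1, and the Dose Escalation Part of the Clinical Trial Summary): "For subsequent cycles, patients will maintain the maximum weekly dose that they achieved in Cycle 1, as shown in Table 2".
- **Rule B** (Section 6.2.2, Study continuation, and the same heading in the Summary): "The dose given in the second or subsequent cycles will be the last dose given in the previous cycle".

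Shortly before Rule A, the same text states that after lead-in "each patient will receive a fixed dose until the end of treatment, unless the dose needs to be decreased for safety reasons". Section 6.5.2 defines the size of a reduction ("Dose modifications, if required, will be a reduction of 1 step (Table 4) from the last administered dose") and the target dose ("The target dose is the dose that will be given every 7 days after lead-in dosing"). For the Dose Escalation Part, the Summary adds that "a patient may begin Cycle 2 provided he or she did not experience a DLT", and Section 6.7.5 repeats this condition.

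**The concern.** Rule A looks back to the highest Cycle 1 dose and Rule B to the most recent dose. For a patient reduced after toxicity these are different doses, and no sentence ranks the rules. Two sites could each follow the protocol as they read it and give the same patient different doses from Cycle 2 on.

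This is a first-in-human T-cell engager. The amendment itself was prompted by a full clinical hold and by doubt about what the first 3 patients had received, so the dosing instruction should have only one reading. Later toxicity also matters to the design: Section 6.3 allows cumulative toxicity after the DLT window to inform escalation and dose selection.

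There is a smaller analytical effect. SAP Section 4.7.1.2 builds the planned dose from the intended dose on the CRF and counts a reduction when the dose taken is below 80% of it. If sites enter the intended dose under different rules, the relative dose intensity and the reduction flag differ for the same infusion.

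**Working it through.** The plan offers no figure to reproduce, and the entries in Tables 1, 2 and 4 are blacked out. The check is therefore to ask in which patients the rules diverge, and then whether other text settles the difference.

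**Step 1: where they diverge.** Let *s* be the dose step reached after lead-in. Rule A gives the Cycle 1 maximum; Rule B gives the last dose of the previous cycle.

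| Patient entering the next cycle | Rule A | Rule B | Difference |
|---|---|---|---|
| 1. Reached *s* in Cycle 1, never changed | *s* | *s* | none |
| 2. Reached *s*, then reduced 1 step in Cycle 1 | *s* | *s* − 1 | 1 step |
| 3. At *s* through Cycle 1, reduced 1 step in Cycle 2, entering Cycle 3 | *s* | *s* − 1 | 1 step |
| 4. Reached *s*, but the last infusion was a restarted lead-in dose | *s* | the lead-in dose | *s* minus the lead-in dose |

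**Step 2: is patient 2 a real path?** Yes.

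- Section 6.5.4 requires a 1-step reduction for Grade 4 neutropenia resolved within 10 days of the last infusion. Section 6.2.1 makes Grade 4 neutropenia a DLT only if it is unresolved within 14 days. An event that starts after the last infusion and is gone by day 10 has lasted at most 10 days, and 10 < 14, so it is not a DLT on this criterion. The patient may begin Cycle 2.
- Grade 3 febrile neutropenia also triggers a reduction under Section 6.5.4, but the hematological DLT list in Section 6.2.1 names only Grade 4.
- For Grade 3 nonhematological events resolved within 10 days, Section 6.5.5 says "treatment will be continued with a dose reduction of 1 step (Section 6.5.2) after recovery". Most such events are DLTs. A laboratory abnormality without clinical consequences that resolves within 5 days is not.

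**Step 3: is patient 4 a real path?** Yes, but a narrower one. If the Day 29 infusion is omitted, the gap from Day 22 to Day 36 is 36 − 22 = 14 days. This is at least 10, so Section 6.2.2 requires a restart with lead-in dosing on Day 36, and the last Cycle 1 dose is a lead-in dose.

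**Step 4: does other text settle it?**

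- For a reduced patient, the safety exception runs to the end of treatment, and Section 6.5 opens by making planned doses subject to modification for adverse events. Both point to keeping the reduction.
- Rule A does not repeat that exception, and Section 6.5 nowhere says that a reduction carries over from one cycle to the next.
- "Do not escalate past the target dose", or a close variant, appears in some reduction rows: Grade 3 CRS in Table 6, the 11-to-14-day column of Table 7, the 21-day-or-less column of Table 8, and parts of Table 9. It is missing from Table 5 Grade 3 or 4, from prolonged Grade 2 CRS in Table 6, and from the ≤10-day and >14-day columns of Table 7. It is also missing from the >21-day column of Table 8 and from the Grade 3 cell of Table 9 for events resolved in under 10 days.
- The neutropenia example in Step 2 falls in the ≤10-day column of Table 7, one of the places without the limit.
- For a patient in a restarted lead-in, the sentence after Rule B in Section 6.2.2 and the target-dose definition in Section 6.5.2 largely give the answer: finish the lead-in, then give the target dose.

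**Step 5: exposure per affected patient.** Cycle 1 has 6 infusions in DL1 and DL2 and 7 from DL3 on; Cycle 2 has 6. For a patient reduced in Cycle 1, 6 of 6 + 6 = 12, or 6 of 7 + 6 = 13, infusions in the first two cycles fall under the disputed rule, and so does every later cycle. This counts the schedule. It does not estimate how often doses would actually differ.

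**The case against.** The strongest reply is that Rule A and Table 2 only set out the planned schedule by dose level, and that Section 6.5 governs departures from it. The safety exception stands in the same text as Rule A. Section 6.2.2 refers to Section 6.5 for retreatment just before Rule B, and Section 6.7.5 does so for starting a new cycle. Where a return to the planned dose is intended, the tables say so, as for Grade 2 events in Table 9 and short Grade 2 CRS in Table 6. Silence elsewhere can fairly be read as no return.

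Most of this stands. A reader might infer that the protocol sends a patient reduced for toxicity back to the higher dose. The documents do not support that: it requires reading Rule A apart from its own paragraph and from Section 6.5, and with Table 2 blacked out no entry or footnote there can be cited for it. Nor do they support saying that a patient in a restarted lead-in would be held at a lead-in dose indefinitely, since Sections 6.2.2 and 6.5.2 point the other way.

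A reader might also infer damage to the Expansion Part response rate. Both rules stand in Dose Escalation text, and the Summary sets the Expansion dose by the selected dose. SAP Sections 4.3 and 4.4 state that no efficacy endpoint will be analyzed because the trial ended early.

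The DLT condition for Cycle 2 and the waiver of modification for disease-related events reduce the number affected further. What the reply does not remove is the contradiction itself: two current sentences, each stated twice, with no order of precedence.

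**Conclusion.** The contradiction holds as a matter of text. Rules A and B give different doses to any patient whose last dose is not the Cycle 1 maximum, chiefly one reduced for a non-DLT event in Cycle 1 or reduced in Cycle 2 or later. On the whole text, keeping a reduction is the more natural reading. That describes the wording and does not recommend a clinical rule. Re-escalation remains a possible misreading, because the exception is not repeated, persistence across cycles is not stated, and the limit on escalation is missing from several reduction rows.

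The difference is 1 step per infusion after a single 1-step reduction, and it lasts for all 6 infusions of the next cycle and beyond. The size of a step in ng/kg and the number of patients affected cannot be determined from the documents. The consequences concern safety and the exposure summaries; there is none for sample size, alpha or power. The conclusion assumes that no note in the blacked-out tables or in the Pharmacy Manual, which is not among the documents, already settles the point.

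**What to change.** Reconcile the four sentences (the two in the Clinical Trial Summary and those in Sections 6.2.1 and 6.2.2) with each other and with Section 6.5, so that one rule appears in all four places. The rule should state how it applies to a patient whose dose was reduced in Cycle 1 or later, and to a patient in a restarted lead-in at the end of a cycle. It should cross-refer to Section 6.5.2. The reduction rows of Tables 5 to 9 should be made consistent on whether the limit on later escalation applies. The sponsor and its clinical team decide which rule holds.

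For the analysis, the SAP should say which dose counts as intended from Cycle 2 on, so that relative dose intensity and the 80% reduction flag are derived in the same way for every patient.

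The cost is a few sentences in the protocol, consistent table entries and one line in the SAP. No patients, visits or procedures are added.

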# 6.2.2 Dose-limiting toxicity

The DLT observation period is 42 days from the first administration of IMP in the first cycle, with administration of IMP on Day 1, Day 4 (DL  $\geq$ 3), Day 8, and weekly thereafter. A new dose level may begin 42 days after the last patient at a particular dose level receives his or her first dose of SAR440234.

The goal is to treat 3 patients per dose level in order to follow a 3 + 3 design. For a given dose level, the second and third patients will be treated after the first patient at this dose level has been treated for 1 week. In the event of a DLT, the dose level will be expanded to a total of 6 patients, who will be treated at the same dose level that the DLT occurred (3 + 3 design). If 1 of the 6 patients experience an IMP-related DLT at the dose level, the dose escalation will proceed with 3 patients per dose level. If  $\geq 2$  of 6 patients experience an IMP-related DLT, the MAD has been reached and the dose escalation will be stopped. The dosing plan for DL1 to DL8 is summarized in Table 3.

Table 3 - Dose Escalation Part from DL1 to DL8

DLT observed at Cycle 1, in the first 3 patients	DLT observed in the whole cohort
DLT in $0/3 \rightarrow$ escalate to the next dose level	-
DLT in 1/3 $\rightarrow$ add 3 more patients at the same level	
 
- 1 DLT/ 6 patients → escalate to the next level
 
- ≥2 DLTs/ 6 patients → define MAD
 

DLT in $\geq$ 2/3 $\rightarrow$ no additional patients	Defines MAD

DLT=dose-limiting toxicity; MAD=maximum administered dose

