### **Dose-limiting toxicity**

The DLT observation period is 42 days from the first administration of IMP in the first cycle, with administration on Day 1, Day 4 (DL  $\geq$ 3), Day 8, and weekly thereafter. A new dose level may begin after the DLT observation period of the previous dose level is finished. The goal is to treat 3 patients per dose level in order to follow a 3 + 3 design. DL3 to DL8 will include 3 patients per dose level. In the event of a DLT, the dose level will be expanded to a total of 6 patients, who will be treated at the same dose level that the DLT occurred (3 + 3 design). If 1 of the 6 patients experience an IMP-related DLT at the dose level, the dose escalation will proceed with 3 patients per dose level. If  $\geq$ 2 of 6 patients experience an IMP-related DLT, the MAD has been reached and the dose escalation will be stopped.

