### 6.3 MAXIMUM ADMINISTERED DOSE / MAXIMUM TOLERATED DOSE

The dose escalation will end when the MAD is reached, which will be defined as the dose at which ≥33% of evaluable patients have experienced an IMP-related DLT during the DLT observation period in a cohort of 6 patients.

The MTD will be defined as the highest dose level at which no more than 1 patient of a maximum of 6 patients experienced an IMP-related DLT.

The patient population evaluable for MTD determination in the Dose Escalation Part will consist of all patients who receive at least 5 out of 6 weekly IV administrations of SAR440234 in DL1 and DL2, patients who receive at least 6 out of 7 IV administrations of SAR440234 in DL  $\geq$ 3, and patients who discontinue the IMP before completion of Cycle 1 because of a DLT.

A patient who discontinues the IMP before the end of the DLT observation period or does not receive the planned dose for any reason other than DLT, will be replaced by enrolling another patient. The first 3 patients treated during the Dose Escalation Part of TED15138 will be replaced. Another 3 patients will be enrolled in DL1 and the trial will proceed according to the 3+3 design.

The dose level below the MAD will be considered the preliminary MTD, providing DLTs are observed in fewer than 2 of 6 treated patients (or fewer than one-third if more than 6 patients) at that dose level. Intermediate dose levels may be evaluated according to Study Committee recommendations. The MTD is generally the highest dose level at which at most 1 patient of a dose level cohort experiences a DLT.

Although the dose escalation process is guided by the safety evaluation during the DLT observation period, cumulative or irreversible toxicities observed in subsequent administrations should also be considered for the dose escalation and dose selection decisions (ie, smaller increases in dose, expansion of a given dose level, or an intermediate dose level), upon agreement between the participant Investigators and the Sponsor.

In the absence of an MTD, pharmacokinetic and pharmacodynamic parameters may help to define the recommended dose of SAR440234 to be tested in the expansion cohort part of the study.

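### The 3+3 stopping rule contradicts itself for two or more DLTs among the first three patients: the protocol text and Section 6.3 lead to six patients, Table 3 stops at three

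*Protocol*

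**What the plan says.** Four places in the protocol govern what happens when DLTs occur in the first three patients of a dose level.

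- **Section 6.2.2, running text.** "In the event of a DLT, the dose level will be expanded to a total of 6 patients". The text then gives two outcomes, both on a denominator of six. One IMP-related DLT leads to escalation. For two or more of six, it says that if that many "patients experience an IMP-related DLT, the MAD has been reached and the dose escalation will be stopped".
- **Clinical Trial Summary, Dose-limiting toxicity.** The same trigger, in the same words and again with no exception. The summary carries no copy of Table 3.
- **Section 6.2.2, Table 3.** Three branches. With 0 of 3, escalate. With 1 of 3, "add 3 more patients at the same level". With 2 or more of 3, "no additional patients", and this result defines the MAD.
- **Section 6.3.** Escalation ends at the MAD, which is the dose at which "≥33% of evaluable patients have experienced an IMP-related DLT during the DLT observation period in a cohort of 6 patients".

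Section 6.2.2 presents Table 3 as a summary of the dosing plan. Nothing says whether the text or the table prevails if they differ. SAP Section 2 does not restate the escalation rule, so it does not settle the matter.

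**The concern.** The branch with two or more DLTs among the first three is where a 3+3 rule has to be clearest, because that level has already shown the number of events that stops escalation. Here three statements lead to six patients and one stops at three.

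Two consequences follow from a literal reading. A cohort stopped at three under Table 3 does not satisfy the Section 6.3 definition of the MAD, although reaching the MAD is what ends escalation. A cohort handled under the text goes on to treat three more patients at a level where the stopping count has been reached.

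The setting gives this weight. The study is a first-in-human trial of a T-cell engager. Section 4.6 names severe cytokine release syndrome as an anticipated risk, and Grade 3 or 4 events of that kind are DLTs. Amended Protocol 03 restarted the study after a full clinical hold and moved to 3+3 throughout in order to detect safety signals more accurately.

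**Working it through.** **Inputs.** The expansion trigger and the two-of-six stopping count come from the 6.2.2 text, the three-patient branch from Table 3, and the 33% threshold from Section 6.3. The true DLT rate p is not in the documents. It is an assumption here, shown from 10% to 50%.

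**Step 1: the plan's own threshold.** 1/6 = 16.7% and 2/6 = 33.3%. The 33% threshold in a cohort of six is therefore the same as two or more of six, and Sections 6.2.2 and 6.3 agree on that.

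**Step 2: the six-patient condition does real work.** 1/3 = 33.3% also reaches 33%. If the condition were simply deleted from Section 6.3, one DLT in three would be a MAD, while Table 3 adds three patients in that case. So the phrase cannot be passed over as loose wording.

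**Step 3: can three more patients change the decision?** Take the DLT count in the first three and add 0 to 3 from the next three.

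| DLTs in first 3 | Possible total of 6 | Possible decisions |
|---|---|---|
| 1 | 1 to 4 | escalate or MAD |
| 2 | 2 to 5 | MAD only |
| 3 | 3 to 6 | MAD only |

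After two or three DLTs, every outcome meets two of six.

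**Step 4: probability of escalating.** Escalation needs 0 of 3, or 1 of 3 followed by 0 of 3. Under either rule,

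P(escalate) = (1−p)³ + 3p(1−p)² × (1−p)³.

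**Step 5: how often the rules diverge, and the cost.**

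- P(2 or more of 3) = 3p²(1−p) + p³.
- Expected patients per level, Table 3: 3 + 3 × 3p(1−p)².
- Expected patients per level, text: 3 + 3 × [1 − (1−p)³].
- Expected further DLTs each time the text adds three patients: 3p.

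| Assumed p | P(≥2 of first 3) | P(escalate), both rules | Patients per level, Table 3 | Patients per level, text | Further DLTs per occurrence |
|---|---|---|---|---|---|
| 0.10 | 0.028 | 0.906 | 3.73 | 3.81 | 0.30 |
| 0.20 | 0.104 | 0.709 | 4.15 | 4.46 | 0.60 |
| 0.33 | 0.255 | 0.434 | 4.33 | 5.10 | 0.99 |
| 0.40 | 0.352 | 0.309 | 4.30 | 5.35 | 1.20 |
| 0.50 | 0.500 | 0.172 | 4.13 | 5.63 | 1.50 |

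For example, at p = 0.33: 3 × 0.1089 × 0.67 + 0.0359 = 0.255. The difference in expected patients is three times this probability, 3 × 0.2548 = 0.76.

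**The case against.** **The text and table can be read together.** The 6.2.2 sentence speaks of a single DLT, labels itself 3+3, and the paragraph ends by pointing to Table 3, which separates the three branches. On that view the sentence describes the 1-of-3 branch and the table supplies the one it omits. This is a fair reading of 6.2.2 alone. It does not repair the summary, which has no table, or Section 6.3, which ties the MAD to six patients.

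**A reader might infer that a site following the text would enrol three more patients on its own.** The documents do not support that. Section 9.1.1 requires DLTs to be reported within 24 hours and has the Study Committee review their relationship to the IMP. Section 6.10 gives that committee the escalation decision and has cohort expansion discussed and documented. Section 12.2 has each patient's dose level confirmed in writing to the investigator. These controls reduce the risk, but the committee works from the same conflicting passages.

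**Relatedness matters.** The trigger in the text is any DLT, while the stopping count is of IMP-related DLTs. If one of the first two were later judged unrelated, three further patients could be informative. The claim that they cannot change the decision therefore holds only for confirmed IMP-related DLTs.

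**A reader might also infer that the size of the MTD cohort is undefined**, because the preliminary MTD is stated as "providing DLTs are observed in fewer than 2 of 6 treated patients" while Table 3 escalates after 0 of 3. That does not hold. Section 6.3 also caps the MTD at one IMP-related DLT among at most six patients, and adds a general description of one DLT at most per cohort with no size attached. A level with three patients and no DLT satisfies both. Nor does the recommended Phase 2 dose follow mechanically from that cohort: the Study Committee chooses it, and Section 6.3 allows for later toxicity, intermediate levels and expansion of a level.

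**The trial ended early.** SAP Sections 4.3 and 4.9 say so. This limits the practical effect now, but it does not remove the contradiction from the protocol.

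**Conclusion.** The contradiction is real and is in the current text. The summary, the 6.2.2 text and the 6.3 definition lead to six patients; the last row of Table 3 stops at three.

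Its effect is confined to exposure. It would be wrong to conclude that it alters the design's chance of escalating or stopping, because that probability is identical under both readings at every DLT rate. What differs is three more patients each time two or more of the first three have a DLT. The chance of that at a given level runs from 2.8% at an assumed rate of 10% to 50% at an assumed rate of 50%, with 0.3 to 1.5 further DLTs expected per occurrence.

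These figures rest on three assumptions: the DLT rates are illustrative, patients' outcomes are independent with a common rate within a level, and the first DLTs are confirmed as IMP-related. The finding that the decision is already fixed needs only the last of these.

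**What to change.** Reconcile the Clinical Trial Summary, the 6.2.2 text, Table 3 and the MAD definition in Section 6.3, so that one rule is printed for two or more DLTs among the first three patients. Which rule applies is for the sponsor to decide.

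The 6.3 definition must then agree with the rule chosen. Deleting its six-patient condition is not enough, because one DLT in three would then also reach 33%. The same edit should say whether the expansion trigger, like the stopping count, refers to IMP-related DLTs.

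The cost is a few words in four places, with no change to the analysis. If the protocol will not be amended again because the trial has closed, the study report should state which rule was applied to any level where this case arose.
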